**Wilcoxon Signed Rank test with 95% CI for Median:**

```
proc univariate data=bleedtp cipctldf;  
var chg;  
run;
```

Statistical Analysis Plan

Catalyst Biosciences, Inc. Protocol # MAA-201

Version 2.0

Syneos Health #1009647

## APPENDIX II SCORING FOR EQ-5D-5L DESCRIPTIVE SYSTEM AND VAS

The EQ-5D-5L descriptive system should be scored, for example, as follows:

Under each heading, please tick the ONE box that best describes your health TODAY		Levels of perceived problems are coded as follows:	
MOBILITY			
I have no problems in walking about			
I have slight problems in walking about			
I have moderate problems in walking about			Level 1 is coded as a '1'
I have severe problems in walking about			
I am unable to walk about			
SELF-CARE			
I have no problems washing or dressing myself			
I have slight problems washing or dressing myself			Level 2 is coded as a '2'
I have moderate problems washing or dressing myself			
I have severe problems washing or dressing myself			
I am unable to wash or dress myself			
USUAL ACTIVITIES (e.g. work, study, housework, family or leisure activities)			
I have no problems doing my usual activities			
I have slight problems doing my usual activities			Level 3 is coded as a '3'
I have moderate problems doing my usual activities			
I have severe problems doing my usual activities			
I am unable to do my usual activities			
PAIN / DISCOMFORT			
I have no pain or discomfort			
I have slight pain or discomfort			Level 4 is coded as a '4'
I have moderate pain or discomfort			
I have severe pain or discomfort			
I have extreme pain or discomfort			
ANXIETY / DEPRESSION			
I am not anxious or depressed			
I am slightly anxious or depressed			
I am moderately anxious or depressed			
I am severely anxious or depressed			Level 5 is coded as a '5'
I am extremely anxious or depressed			

This example identifies the health state '12345'.

**NB:** There should be only ONE response for each dimension

**NB:** Missing values can be coded as '9'.

**NB:** Ambiguous values (e.g. 2 boxes are ticked for a single dimension) should be treated as missing values.

[figure not shown]
Statistical Analysis Plan

Catalyst Biosciences, Inc. Protocol # MAA-201

Version 2.0

Syneos Health #1009647

The EQ VAS should be scored, for example, as follows:

**NB: Missing values should be coded as '999'.**

**NB: If there is a discrepancy between where the respondent has placed the X and the number he/she has written in the box, administrators should use the number in the box.**

Statistical Analysis Plan

Catalyst Biosciences, Inc. Protocol # MAA-201

Version 2.0

Syneos Health #1009647

## APPENDIX III SCORING METHOD FOR HEMOPHILIA A QUALITY OF LIFE QUESTIONNAIRE

The 46-items of the Haem-A-QoL are scored into 10 scales:

- Physical health (PHYS) - 5 items
- Feelings (FEEL) - 4 items
- View of yourself (VIEW) - 5 items
- Sports and Leisure (SPORT) - 5 items
- Work and school (WORK) - 4 items
- Dealing with Haemophilia (DEAL) - 3 items
- Treatment (TREAT) - 8 items
- Future (FUTURE) - 5 items
- Family planning (FAMPL) - 4 items
- Partnership and sexuality (SEXUAL) - 3 items

Responses range from 'Never' (1) to 'All of the time' (5), with several items having a 'Not applicable' option that is scored as a (0). Higher scores are reflective of greater impairment or poorer health-related quality of life.

In order to have all of the responses scored in the same direction, several items will have to be reverse-scored. The following items should be reverse scored:

- VIEW - 2nd item
- VIEW - 5th item
- SPORT - 3rd item
- WORK - 1st item
- WORK - 2nd item
- DEAL - 1st item
- DEAL - 2nd item
- DEAL - 3rd item
- TREAT - 8th item
- FUTURE - 2nd item

The reverse scoring for those items is as follows: (1=5), (2=4), (3=3), (4=2), and (5=1). Any (0) will be recoded as missing data for the purposes of scale scoring. In listings of frequencies, the number of patients reporting 'Not applicable' can also be displayed.

These reverse scored items will be given a new label (e.g., view2x) and used instead of the original items when calculating the scale score.

Several additional items are recoded into the same scores but will be given a different label for future use. These are:

- SPORT - 1st item
- SPORT - 2nd item

**Statistical Analysis Plan**

Catalyst Biosciences, Inc. Protocol # MAA-201

Version 2.0

Syneos Health #1009647

- SPORT - 4th item
- SPORT - 5th item
- WORK - 3rd item
- WORK - 4th item
- FAMPL - 1st item
- FAMPL - 2nd item
- FAMPL - 3rd item
- FAMPL - 4th item

The recoding for these items is: (1=1) (2=2) (3=3) (4=4) and (5=5).  
The recoded items will be given a new label (e.g., sport1m) and used in future analyses.

Scales can be calculated if  $\geq 50\%$  of items have been answered. As the questionnaire is being administered electronically and patients are not able to skip items, there should not be any missing items. As patients can answer “Not applicable”, however, to questions in the SPORT, WORK, and FAMPL domains, items could be treated as missing. In this case, the minimum number of items that needs to be completed and not responded to as “Not applicable” is:

- SPORT: 3
- WORK: 2
- FAMPL: 2

Following the recoding, the sum of each scale should be computed. The computation of these scales is as follows:

- PHYS is the sum of the 5 items from the scale (phys1, phys2, phys3, phys4, phys5).
- FEEL is the sum of the 4 items from the scale (feel1, feel2, feel3, feel4).
- VIEW is the sum of items 1, 3, and 4 and reverse-scored items 2 and 5 from the scale (view1, view2x, view3, view4, view5x).
- SPORT is the sum of items 1, 2, 4, 5 and reverse-scored item 3 from the scale (sport1, sport2, sport3x, sport4, sport5).
- WORK is the sum of items 3, 4 and reverse-scored items 1 and 2 from the scale (work1x, work2x, work3, work4).
- DEAL is the sum of reverse-scored items 1, 2, and 3 from the scale (deal1x, deal2x, deal3x).
- TREAT is the sum of items 1 through 7 and reverse-scored item 8 from the scale (treat1, treat2, treat3, treat4, treat5, treat6, treat7, treat8x).
- FUTURE is the sum of items 1, 3, 4, 5 and reverse-scored item 2 from the scale (future1, future2x, future3, future4, future5).
- FAMPL is the sum of items 1 through 4 from the scale (fampl1, fampl2, fampl3, fampl4).

**Statistical Analysis Plan**

Catalyst Biosciences, Inc. Protocol # MAA-201

Version 2.0

Syneos Health #1009647

- SEXUAL is the sum of items 1, 2, and 3 from the scale (sexual1, sexual2, sexual3).

A Total Haem QOL score (HAETOTAL) is calculated by summing all of the previously mentioned raw and reverse coded items in the scales above (phys1, phys2, phys3, phys4, phys5, feel1, feel2, feel3, feel4, view1, view2x, view3, view4, view5x, sport1, sport2, sport3x, sport4, sport5, work1x, work2x, work3, work4, deal1x, deal2x, deal3x, treat1, treat2, treat3, treat4, treat5, treat6, treat7, treat8x, future1, future2x, future3, future4, future5, fampl1, fampl2, fampl3, fampl4, sexual1, sexual2, sexual3).

The scores for each scale should then be standardized onto a 100-point scale. This can be done as follows:

- PHYS\_Z = summing the raw score of the items in the PHYS scale and taking the mean of those items, subtracting one (1) from that number and dividing by four (4) which is the range for the scale. This number is then multiplied by 100. As an example,  $PHYS\_Z = (MEAN (phys1, phys2, phys3, phys4, phys5) - 1) / 4 * 100$ .
- FEEL\_Z = summing the raw score of the items in the FEEL scale and taking the mean of those items, subtracting one (1) from that number and dividing by four (4) which is the range for the scale. This number is then multiplied by 100.  $(MEAN (feel1, feel2, feel3, feel4) - 1) / 4 * 100$ .
- VIEW\_Z = summing the raw and reverse score of the items in the VIEW scale and taking the mean of those items, subtracting one (1) from that number and dividing by four (4) which is the range for the scale. This number is then multiplied by 100.  $(MEAN (view1, view2x, view3, view4, view5x) - 1) / 4 * 100$ .
- SPORT\_Z = summing the raw and reverse scores of the items in the SPORT scale and taking the mean of those items, subtracting one (1) from that number and dividing by four (4) which is the range for the scale. This number is then multiplied by 100.  $(MEAN (sport1m, sport2m, sport3x, sport4m, sport5m) - 1) / 4 * 100$ .
- WORK\_Z = summing the raw and reverse scores of the items in the WORK scale and taking the mean of those items, subtracting one (1) from that number and dividing by four (4) which is the range for the scale. This number is then multiplied by 100.  $(MEAN (work1x, work2x, work3m, work4m) - 1) / 4 * 100$ .
- DEAL\_Z = summing the raw and reverse scores of the items in the DEAL scale and taking the mean of those items, subtracting one (1) from that number and dividing by four (4) which is the range for the scale. This number is then multiplied by 100.  $(MEAN (deal1x, deal2x, deal3x) - 1) / 4 * 100$ .
- TREAT\_Z = summing the raw and reverse scores of the items in the TREAT scale and taking the mean of those items, subtracting one (1) from that number and dividing by four (4) which is the range for the scale. This number is then multiplied by 100.  $(MEAN (treat1, treat2, treat3, treat4, treat5, treat6, treat7,$

**Statistical Analysis Plan**

Catalyst Biosciences, Inc. Protocol # MAA-201

**Version 2.0**

**Syneos Health #1009647**

$(\text{treat8x}-1)/4*100$ .

- FUTURE\_Z = summing the raw and reverse scores of the items in the FUTURE scale and taking the mean of those items, subtracting one (1) from that number and dividing by four (4) which is the range for the scale. This number is then multiplied by 100.  $(\text{MEAN}(\text{future1}, \text{future2x}, \text{future3}, \text{future4}, \text{future5})-1)/4*100$ .
- FAMILY\_Z = summing the raw score of the items in the FAMILY scale and taking the mean of those items, subtracting one (1) from that number and dividing by four (4) which is the range for the scale. This number is then multiplied by 100.  $(\text{MEAN}(\text{fampl1m}, \text{fampl2m}, \text{fampl3m}, \text{fampl4m})-1)/4*100$ .
- RELAT\_Z = summing the raw score of the items in the RELAT scale and taking the mean of those items, subtracting one (1) from that number and dividing by four (4) which is the range for the scale. This number is then multiplied by 100  $(\text{MEAN}(\text{sexual1}, \text{sexual2}, \text{sexual3})-1)/4*100$ .

Finally, a Total Haem-A-QOL transformed score (HAEMA\_Z) should be computed by summing the raw and reverse scores of all of the items, taking the mean of those items, subtracting one (1) from that number and dividing by four (4) which is the range for the scale. This number is then multiplied by 100

$\text{HAEMA\_Z} = (\text{MEAN}(\text{phys1}, \text{phys2}, \text{phys3}, \text{phys4}, \text{phys5}, \text{feel1}, \text{feel2}, \text{feel3}, \text{feel4}, \text{view1}, \text{view2x}, \text{view3}, \text{view4}, \text{view5x}, \text{sport1m}, \text{sport2m}, \text{sport3x}, \text{sport4m}, \text{sport5m}, \text{work1x}, \text{work2x}, \text{work3m}, \text{work4m}, \text{deal1x}, \text{deal2x}, \text{deal3x}, \text{treat1}, \text{treat2}, \text{treat3}, \text{treat4}, \text{treat5}, \text{treat6}, \text{treat7}, \text{treat8x}, \text{future1}, \text{future2x}, \text{future3}, \text{future4}, \text{future5}, \text{fampl1m}, \text{fampl2m}, \text{fampl3m}, \text{fampl4m}, \text{sexual1}, \text{sexual2}, \text{sexual3})-1)/4*100$ .

Statistical Analysis Plan

Catalyst Biosciences, Inc. Protocol # MAA-201

Version 2.0

Syneos Health #1009647

## APPENDIX IV SCORING METHOD FOR HAL QUESTIONNAIRE

### Scoring system

Scores can be calculated for each of the seven domains of the HAL. Additionally, three component scores can be calculated (Activities involving the Upper Extremities, Basic activities involving the Lower Extremities and Complex activities involving the Lower Extremities) as well as an overall score. Before summarizing the individual item scores, recoding is required (see Table 1); a higher raw score represents more functional limitations; possible scoring ranges are given (Table 2).

Normalized scores for the domains, components, and the full questionnaire can also be obtained. Missing values are controlled for and the possible scores range from 0 to 100, where 0 represents the worst possible functional status and 100 the best possible functional status (Table 3).

Table 1: Recoding

Score	Recode	Meaning
8	0	N/A
1	6	Impossible
2	5	Always problems
3	4	Mostly problems
4	3	Sometimes problems
5	2	Rarely problems
6	1	Never problems

Table 2: Scores

Score		Items	Score range
Lying / sitting / kneeling / standing	LSKS	1-8 (8)	8 - 48
Functions of the legs	LEGS	9-17 (9)	9 - 54
Functions of the arms	ARMS	18-21 (4)	4 - 24
Use of transportation	TRANS	22-24 (3)	3 - 18
Self care	SELFC	25-29 (5)	5 - 30
Household tasks	HOUSEH	30-35 (6)	6 - 36
Leisure activities and sports	LEISPO	36-42 (7)	7 - 42
Upper Extremity Activities	UPPER	* (9)	9 - 54
Basic Lower Extremity Activities	LOWBAS	** (6)	6 - 36
Complex Lower Extremity Activities	LOWCOM	*** (9)	9 - 54
Sum score	SUM	1-42 (42)	42 - 252

\* Items for UPPER-component: 18, 19, 20, 21, 25, 26, 27, 28, 29. (9 items)

\*\* Items for LOWBAS-component: 8, 9, 10, 11, 12, 13. (6 items)

\*\*\* Items for LOWCOM-component: 3, 4, 6, 7, 14, 15, 16, 17, 22. (9 items)

Statistical Analysis Plan

Catalyst Biosciences, Inc. Protocol # MAA-201

Version 2.0

Syneos Health #1009647

Table 3: Normalization

Score	Normalisatie
LSKS	$100 - ((\sum_{1-8} - \text{valid}) * (100/(5 * \text{valid})))$
LEGS	$100 - ((\sum_{9-17} - \text{valid}) * (100/(5 * \text{valid})))$
ARMS	$100 - ((\sum_{18-21} - \text{valid}) * (100/(5 * \text{valid})))$
TRANS	$100 - ((\sum_{22-24} - \text{valid}) * (100/(5 * \text{valid})))$
SELFC	$100 - ((\sum_{25-29} - \text{valid}) * (100/(5 * \text{valid})))$
HOUSEH	$100 - ((\sum_{30-35} - \text{valid}) * (100/(5 * \text{valid})))$
LEISPO	$100 - ((\sum_{36-42} - \text{valid}) * (100/(5 * \text{valid})))$
UPPER	$100 - ((\sum_{18-21;25-29} - \text{valid}) * (100/(5 * \text{valid})))$
LOWBAS	$100 - ((\sum_{8-13} - \text{valid}) * (100/(5 * \text{valid})))$
LOWCOM	$100 - ((\sum_{3-7;14-17;22} - \text{valid}) * (100/(5 * \text{valid})))$
SUM	$100 - ((\sum_{1-42} - \text{valid}) * (100/(5 * \text{valid})))$

"valid" = number of items scored within the specific domain/component.  
 Items with "n/a"-response are to be considered **NOT** valid

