### 8.3.4 Analysis of Hemophilia Activities List (HAL)

HAL contains 7 domains: Lying/sitting/kneeling/standing, functions of the legs, functions of the arms, use of transportation, self-care, household tasks and leisure activities and sports. Additionally, three component scores can be calculated (upper extremity activities, basic lower extremity activities and complex lower extremity activities) as well as an overall score. Normalized score will be calculated for each of the 7 domains, 3 component scores and total score. For detailed scoring method, please see [Appendix IV](#).

Descriptive analyses for normalized score and change from baseline normalized scores for HAL will be provided by study part for each of the dimensions by study part, dose level and visit.

The one sample Wilcoxon signed rank test for a single group data will be used to compare the baseline HAL result vs the last post-baseline assessment at the final treatment dose HAL result, independently for each dose level in Part 2. A 95% Confidence interval for the median change from baseline value at the last post-baseline assessment at the final treatment dose will also be obtained. Sample SAS code can be found in Appendix I.

Statistical Analysis Plan

Catalyst Biosciences, Inc. Protocol # MAA-201

Version 2.0

Syneos Health #1009647

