**Statistical Analysis Plan**

Catalyst Biosciences, Inc. Protocol # MAA-201

Version 2.0

Syneos Health #1009647

Jumping

Item	Score	Recode
Item 9	4	3
Item 10	3	4
Item 11	5	2
Item 12	4	3
Item 13	4	3
Item 14	Invalid	Invalid
Item 15	4	3
Item 16	1	6
Item 17	1	6

Based on the recoded scores, the raw domain score for the LEGS domain is 30 points.

The LOWBAS component encompasses the items 8-13. Item 8 scored 6 points (i.e. "Impossible"), which results in a raw component score of 6+3+4+2+3+3 = 21 points.

To normalize the scores (both domain and component scores), the formulas presented in

Table 3 are used. This results in the following:

LEGS Normalized: Within the domain, 1 item is invalid, resulting in 8 valid responses out of a possible 9. This results in the following formula:

$$100 - ((\sum_{9-17} \text{-valid}) * (100 / (5 * \text{valid}))) = 100 - ((30 - 8) * (100 / (5 * 8))) = 100 - 55 = \mathbf{45 \text{ points}}$$

LOWBAS Normalized: Within the component, no items are invalid, resulting in 6 valid responses out of a possible 6. This results in the following formula:

$$100 - ((\sum_{8-13} \text{-valid}) * (100 / (5 * \text{valid}))) = 100 - ((21 - 6) * (100 / (5 * 6))) = 100 - 50 = \mathbf{50 \text{ points}}$$

Statistical Analysis Plan

[figure not shown]
Catalyst Biosciences, Inc. Protocol # MAA-201

Version 2.0

Syneos Health #1009647

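### The HAL formula for complex lower-extremity activities (LOWCOM) sums ten items including item 5, although the component is defined as nine items without it

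*SAP*

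**What the plan says.** SAP 8.3.4 commits to the component scores: "Normalized score will be calculated for each of the 7 domains, 3 component scores and total score". It plans descriptive summaries of these scores and their change from baseline. It also plans a Wilcoxon signed-rank test of HAL at the last assessment on the final dose against baseline, by dose level, with a 95% confidence interval for the median change. Appendix IV is named as the scoring method.

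Appendix IV makes three statements about LOWCOM that have to fit together:

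- **Definition (Table 2 and its footnote).** "Items for LOWCOM-component: 3, 4, 6, 7, 14, 15, 16, 17, 22. (9 items", with a raw range of 9 to 54.
- **Normalisation (Table 3).** The sum for LOWCOM has the subscript shown in "3-7;14-17;22} - \text{valid".
- **Divisor.** *valid* is the "number of items scored within the specific domain/component"; answers marked not applicable do not count.

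The introduction to the scoring tables says of the normalised scores that "the possible scores range from 0 to 100", with 0 the worst and 100 the best function. Protocol Appendix B prints the same nine-item definition and the same LOWCOM formula.

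**The concern.** The span 3-7 contains five items: 3, 4, 5, 6 and 7. With 14-17 and 22 the formula therefore sums ten items. The definition has nine and leaves out item 5, which is bending forward in the questionnaire printed in Protocol Appendix B. In Table 2 the item list, the item count and the raw range (9 x 1 = 9 to 9 x 6 = 54) agree with each other, so the formula is the odd one out.

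The index notation does not explain the difference. The upper-extremity formula skips a block of items by writing 18-21;25-29, so a gap at item 5 could have been written the same way.

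At stake is whether LOWCOM has one reproducible value. Two programmers working from the same appendix could obtain different scores, and neither of the two ways of coding the printed sum gives the score that Table 2 defines.

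**Working it through.** **Inputs.** All are from SAP Appendix IV: recoded answers run from 1 (never a problem) to 6 (impossible); *valid* and the item lists are as given above. The general formula is

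score = 100 - (sum - valid) x 100 / (5 x valid).

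**Step 1: reproduce the SAP's own examples.**

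- LEGS: "the raw domain score for the LEGS domain is 30 points", with 8 valid items. 100 - (30 - 8) x 100/40 = 100 - 55 = 45, as printed.
- LOWBAS: "which results in a raw component score of 6+3+4+2+3+3 = 21 points", with 6 valid items. 100 - (21 - 6) x 100/30 = 100 - 50 = 50, as printed.

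The general formula is sound. There is no worked LOWCOM example.

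**Step 2: compare item lists with formula indices.** Among the component scores, UPPER (nine items) and LOWBAS (six items) agree between Tables 2 and 3, and so do the domain formulas. LOWCOM has nine items in Table 2 and ten in Table 3. The only difference is item 5.

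**Step 3: literal reading.** Ten items are summed and *valid* = 9, because *valid* counts items within the component as defined. Each recoded point is worth 100/45 = 2.22.

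| Same answer to all items | Nine items, valid 9 (as defined) | Ten items, valid 9 (literal) |
|---|---|---|
| 1 (never) | 100 - (9 - 9) x 100/45 = 100 | 100 - (10 - 9) x 100/45 = 97.8 |
| 3 (sometimes) | 100 - (27 - 9) x 100/45 = 60 | 100 - (30 - 9) x 100/45 = 53.3 |
| 6 (impossible) | 100 - (54 - 9) x 100/45 = 0 | 100 - (60 - 9) x 100/45 = -13.3 |

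Whatever the other answers, the literal score is below the defined score by 2.22 x item 5: from 2.22 x 1 = 2.2 to 2.22 x 6 = 13.3 points. A ten-item sum above 54 gives a negative score. If item 22 is marked not applicable, *valid* is 8, each point is worth 100/40 = 2.5, and the worst score is 100 - (54 - 8) x 2.5 = -15.0.

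**Step 4: change from baseline, literal reading.** With *valid* = 9 at both visits, the error in change is -2.22 x (change in recoded item 5). Item 5 can move by at most 5 categories, so the error is at most 5 x 2.22 = 11.1 points in either direction. It is zero if item 5 does not change.

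**Step 5: alternative reading.** Item 5 is also counted in *valid*, so *valid* = 10 and each point is worth 100/50 = 2. The range is again 0 to 100. Writing S for the sum of the nine defined items, the difference from the defined score is

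[100 - 2 x (S + item 5 - 10)] - [100 - (S - 9) x 100/45] = 2 x (S/9 - item 5).

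It vanishes only when item 5 equals the mean of the other nine. The extremes are:

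- nine items at 1 and item 5 at 6: 90 instead of 100;
- nine items at 6 and item 5 at 1: 10 instead of 0.

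**Step 6: after correction.** Summing items 3-4, 6-7, 14-17 and 22 with *valid* = 9 gives a raw range of 9 to 54 and a normalised range of exactly 0 to 100, as Table 2 and the introduction state.

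**The case against.** The strongest reply is that the negative scores need a hybrid program, one that sums ten items but counts nine. A programmer who uses one item list throughout will not produce them. With nine items the score is right; with ten it stays within 0-100 and equals the defined score whenever all answers are the same. This stands as far as it goes: scores below 0 follow from the SAP's wording of *valid*, not from every possible program. It does not remove the conflict, because the ten-item version still scores a component other than the one defined.

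A reader might also infer that the formula inflates change from baseline. If every item shifts by one category, the literal formula does give 10 x 2.22 = 22.2 points instead of 9 x 2.22 = 20, about 11% too much. But that holds only when item 5 moves with the rest. If item 5 is constant and *valid* is unchanged, the change score is exact; if item 5 moves against the others, change is understated or can even be reversed in sign. The documents support a distortion that depends on item 5, not a general overstatement.

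It can further be said that Table 2 makes the intention clear and that SAP section 17 requires checks of program logic and output. A careful programmer may indeed resolve it. But the two worked examples cover LEGS and LOWBAS, so reproducing them would not reveal the LOWCOM fault, and a consistent ten-item score would look plausible on review.

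Finally, the index is a small subscript, and both appendices reproduce the same source table, so its recurrence is not wholly independent confirmation. The HAL scoring manual is not among the documents either. Internal evidence favours Table 2, but the item set should be confirmed at source.

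**Conclusion.** The LOWCOM formula in Table 3 contradicts the component's definition in Table 2, in both the SAP and the protocol. Under the SAP's own wording of *valid*, with all nine defined items and item 5 answered, each score is 2.2 to 13.3 points too low. Change scores are distorted by up to 11.1 points in either direction, with *valid* the same at both visits. Under the alternative count, scores keep to 0-100 but differ from the defined component by up to 10 points either way. That Table 2 is the correct side rests on its list, count and range agreeing with each other and with the stated 0-100 scale.

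The reach is narrow. LOWCOM is one of eleven HAL scores (seven domains, three components and a total), and SAP 4.3 lists the HAL as an exploratory patient-reported outcome. A reader might take a wrong scoring formula as a threat to the trial's efficacy or safety conclusions; nothing in the plan supports that, since neither the primary bleeding-rate analysis nor the safety analysis uses LOWCOM. It should still be corrected, because the score is planned, summarised and tested.

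**What to change.** In SAP Appendix IV Table 3 and in Protocol Appendix B Table 3, write the LOWCOM sum over items 3-4, 6-7, 14-17 and 22, and state that *valid* is counted over the same nine items. Before programming, confirm the item set against the HAL scoring manual. If the manual includes item 5, correct the Table 2 list, count and range instead, so that the two tables agree.

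A program check that normalised scores lie within 0-100 is optional. It would catch some scores from the ten-over-nine hybrid, namely those that fall below 0, but not a consistent ten-item score.

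The cost is one line in each document and a look at the manual. No new data are needed and nothing changes for patients.
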